5.6.2.1. Overall Summary of AEs

An overall summary of AEs and SAEs will be presented. The number of events (n) and number of participants with events (n, %) will be shown for the following event subcategories:

- Any TEAE
- TEAEs leading to study treatment discontinuation
- Related TEAEs

These statistics will be prepared separately for all AEs and SAEs. Additionally, the number and percentage of participants who died on study will be presented.

5.6.2.2. AEs and SAEs by SOC and PT

The number of TEAEs and TESAEs and the number and percentage of participants with events will be presented by SOC and PT. Patients are counted once in each SOC and PT. Percentages will be based on the total number of treated patients in the treatment group. SOCs will be listed in descending order of frequency of occurrence.

Additional summary tables stratifying AEs by age, gender, and race will also be provided.

5.6.2.3. AEs and SAEs by SOC, PT, and Relationship

The number of TEAEs and TESAEs and the number and percentage of participants with events will be presented by SOC and PT as described above by relationship (related, not related). If a patient has more than 1 occurrence of an AE, the strongest relationship to study treatment will be used in the summary table. SAEs will be summarized similarly.

5.6.2.4. AEs and SAEs by SOC, PT, and Severity

The number of TEAEs and the number and percentage of participants with events will be presented by SOC and PT as described above by toxicity grade (Grade 1, Grade 2, Grade 3, Grade 4, Grade 5). If a patient has more than 1 occurrence of an AE, the most severe occurrence will be used in the summary table.

5.6.2.5. Deaths and Other Significant AEs

Individual listings will be presented for AEs leading to study treatment discontinuation, AEs leading to withdrawal from the study, AEs starting during administration of study intervention, and fatal AEs.

Adverse events of special interest include meningococcal infections as defined in Section 6.1.8. A summary table and a listing of AEs related to meningococcal infections will be provided.

5.6.3. Additional Safety Assessments

5.6.3.1. Laboratory Parameters

Laboratory assessments are defined in Section 10.2 of Protocol ALXN1210-NEPH-202.

Observed values and changes from baseline in clinical chemistry, hematology, and urinalysis will be summarized descriptively by treatment group at baseline and at each postbaseline time point separately for each disease cohort. For laboratory results that can be classified as normal, low, or high based on normal range values, shifts from baseline in classification will be summarized for all study visits. For analysis purposes, laboratory results based upon standardized units will be used.

Box plots will be presented for the following central lab parameters by visit: alanine aminotransferase, aspartate transaminase, and creatinine.

All data will be presented in listings, and a specific listing of abnormal results will be provided.

5.6.3.2. Vital Signs

Vital signs will include systolic and diastolic blood pressure (mmHg), heart rate (beats per minute), respiratory rate (breaths per minute), temperature (degrees Celsius [$^{\circ}\text{C}$] or degrees Fahrenheit [$^{\circ}\text{F}$]), and pulse oximetry (%).

Observed values as well as changes from baseline in body weight and vital signs (blood pressure, heart rate, respiratory rate, and temperature) will be summarized descriptively at each time point by treatment group separately for each disease cohort.

A listing of vital signs will be presented for each disease cohort by treatment group, patient, vital sign, and visit.

5.6.3.3. Electrocardiogram (ECG)

A single 12-lead ECG will be conducted according to the schedule of activities in the protocol to obtain heart rate, PR, QRS, QT and corrected QT (QTc) intervals (QT interval will be corrected for heart rate using Fridericia's formula [QTcF]).

A listing of ECG results will be presented for each disease cohort by treatment group, patient, and visit. Electrocardiograms will be evaluated and summarized as normal, abnormal not clinically significant, or abnormal clinically significant. A shift from baseline to worst on-study ECG table will be presented for ECG results. Observed values and change from baseline in ECG intervals (PR, RR, QT, and QTc) will be summarized descriptively at baseline and each postbaseline time point. The QT interval will be corrected for heart rate using Fridericia's formula (QTcF).

5.6.3.4. Physical Exam

A complete physical examination will include, at a minimum, assessments of the following organs/body systems: skin, head, ears, eyes, nose, throat, neck, lymph nodes, chest, heart, abdomen, extremities, musculoskeletal, and neurological state (with emphasis on presence/degree of edema). An abbreviated physical exam will include, at a minimum, a body-system relevant examination based upon Investigator judgment and participant symptoms.

Adverse changes from baseline in physical examination findings will be classified as AEs and analyzed accordingly.

5.7. Other Analyses

5.7.1. Pharmacokinetic and Pharmacodynamic Analyses

Individual PK/PD data will be collected for all participants. PK analyses will be performed on the PK analysis set and PD analyses will be performed on the PD analysis set.

Serum ravulizumab concentration will be summarized over time with descriptive statistics including the number of observations, arithmetic mean, SD, median, minimum, maximum, coefficient of variation, geometric mean, and geometric coefficient of variation. For the calculation of summary statistics, values below the limit of quantification (BLQ) values will be set to half of the lower limit of quantification (LLOQ) unless a BLQ value falls between 2 measurable values, in which case it will be omitted.

A listing of serum ravulizumab concentration will be presented. BLQ values will be displayed as “< LLOQ.”

Graphs of mean serum ravulizumab concentration-time profiles will be constructed. Graphs of serum concentration-time profiles for individual participants may also be provided. Actual dose administration and sampling times will be used for all calculations.

Descriptive statistics will be calculated for all PD endpoints at each sampling time, as appropriate. The PD effects of ravulizumab will be evaluated by assessing the absolute values and changes and percentage changes from baseline in serum concentrations of total C5 and free C5 over time, as appropriate.

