24-hr urine collection ^e	X											X	X ^f	One collection is needed as soon as possible during Screening. Two collections must be obtained within 2 weeks prior to Week 26 (Section 8.2.1)
Morning spot urine sample ^e	X	X	X	X	X	X	X	X	X ^g	X	X	X		Obtain sample prior to dosing, vaccination, and biopsy
eGFR	X	X	X	X	X	X	X	X	X	X	X	X ^f		One additional blood draw for eGFR (serum creatinine) is required within 2 weeks prior to the Week 26 visit.
Monitor for Renal and Extrarenal SLE Flare ^f		Continuous monitoring										X		Refer to Section 3.2.1 and 3.2.2 for definitions. Document use of additional standard of care therapy and/or repeat biopsy ^f , if applicable.
Blood sample for C3, C4, and CH50	X	X		X			X		X		X	X		
Safety Assessments														
Physical examination	X	X										X		
Abbreviated PE			X	X	X	X	X	X	X	X	X			
Vital signs ^h	X	X	X	X	X	X	X	X	X	X	X			

Table 1: Schedule of Activities During the Initial Evaluation Period: Screening to Week 26 Visit (LN Cohort)

Period	Screening	Initial Evaluation Period											Eval. for Renal Flare and Extrarenal SLE Flare	Notes
Visit	1	2	3	4	5	6	7	8	9	10	11			
Week	Up to 6 W		W1 ^a	W2	W4	W6 ^b	W10	W14	W18	W22	W26/ED ^c			
Days and Window	D -42 to -1	D1	D8 ± 2	D15 ± 3	D29 ± 3	D43 ± 5	D71 ± 5	D99 ± 5	D127 ± 5	D155 ± 5	D183 ± 5			
ECG ⁱ	X											X		
Prior medications and procedures	X													
Concomitant medications, nonpharmacologic therapies, and procedures		Continuous monitoring											X	
Adverse events	Continuous monitoring											X		
Clinical chemistry	X	X	X	X	X	X	X	X	X	X	X	X		
Hematology and coagulation	X	X	X	X	X	X	X	X	X	X	X			
Urinalysis and sediment	X	X	X	X	X	X	X	X	X	X	X	X	Obtain sample from a morning void prior to dosing	
Participant safety card review		X	X	X	X	X	X	X	X	X	X	X	Confirm participants carry safety card at all times	
Pharmacokinetic and Pharmacodynamic Assessments														
Blood samples for PK/PD ^j		B/P	X	T/P	X		T/P		T/P		T	X	Samples can be obtained anytime at ED Visit	
Blood samples for ADA		B			X		T				T		Samples can be obtained anytime at ED Visit	
Exploratory Assessments														
EQ-5D-5L		X					X				X			
SF-36		X					X				X			
FACIT-Fatigue		X									X			

Table 1: Schedule of Activities During the Initial Evaluation Period: Screening to Week 26 Visit (LN Cohort)

Period	Screening	Initial Evaluation Period										Eval. for Renal Flare and Extrarenal SLE Flare	Notes	
Visit	1	2	3	4	5	6	7	8	9	10	11			
Week	Up to 6 W		W1 ^a	W2	W4	W6 ^b	W10	W14	W18	W22	W26/ED ^c			

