^f Renal Flare (as defined in Section 3.2.1) and/or Extrarenal SLE Flare (as defined in Section 3.2.2) may occur at any time through Week 50. Evaluation of Renal Flare requires a UPCR from a spot urine sample that is confirmed on a 24-hr urine collection as well as 2 serum creatinine samples obtained within a 2-week period. Evaluation of Renal and Extrarenal SLE Flare must be performed as soon as possible upon notification to the Investigator of symptom onset. If Renal Flare or Extrarenal SLE Flare occurs between scheduled visits, only the assessments for the Renal Flare/Extrarenal SLE Flare visit are needed. If Renal Flare or Extrarenal SLE Flare occur on a scheduled visit, all scheduled assessments should be performed for that visit as well as any additional assessments required for the evaluation of the flare.

^g Two spot urine samples should be obtained the same morning at Week 18.

^h Vital sign measurements include systolic and diastolic BP, pulse oximetry, heart rate, respiratory rate, and temperature. On dosing days, vital signs will be taken predose.

ⁱ Single 12-lead ECG will be collected at Screening and predose on Day 183 and any time on the ED Visit day. Participants must be supine for approximately 5 to 10 minutes before ECG collection and remain supine but awake during ECG collection.

^j For indicated visits falling on dosing days, PK/PD samples will be collected predose (within 0.5 hours prior to the start of infusion) and at EOI (within 0.5 hours after the EOI from the participant's opposite, noninfused arm). In order to minimize needle sticks to the participant, the predose sample may be drawn through the venous access created for the dose infusion, prior to administration of the dose. As noted, the postdose sample must be drawn from the opposite, noninfused arm. For indicated visits not falling on dosing days, samples may be collected at any time that visit day.

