The proposed dosing regimen is modified from the approved dosing regimen in PNH and aHUS indications to account for the influence of the potential intrinsic factors, such as high levels of proteinuria and complement activation in renal pathology, on antibody PK. This is supported by the PK results from eculizumab clinical trials in idiopathic membranous glomerulopathy (IMG) patients with high proteinuria and rheumatoid arthritis (RA) patients with minimal proteinuria, confirming that patients with IMG had significantly lower drug levels at trough compared to RA patients at the same dosing regimen of 8 mg/kg eculizumab every 2 weeks (trough mean levels of approximately 18.5 μ g/mL in participants with IMG versus 30 to 32 μ g/mL in participants with RA) (Study C99-001 in RA and Study C99-004 in IMG). This observed impact of proteinuria on antibody PK is also in agreement with a clinical study of rituximab in membranous nephropathy with high proteinuria confirming that patients with membranous nephropathy exhibited a shorter half-life, decreased exposures, and increased antibody clearance compared to the reference patient populations ([Fogueri, 2019](#)). In a study of adalimumab in focal segmental glomerulosclerosis (FSGS) patients with proteinuria, a linear relationship was seen between increasing proteinuria and the increase in antibody clearance ([Roberts, 2013](#)). In light of this evidence demonstrating a relationship between proteinuria and antibody clearance, the results from M&S analysis show that the expected increase in ravulizumab clearance, based on mean proteinuria levels of approximately 3 to 4 g/day at baseline for participants in the study, may result in inadequate levels of C5 suppression in patients with ≥ 60 kg body weight using the labeled dosing regimen for PNH/aHUS. Therefore, an optimal dosing regimen should be identified to maintain immediate (after the loading dose), complete and sustained (throughout the entire active treatment course) terminal complement inhibition in all participants for the proposed study.

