8.7. Pharmacokinetics and Pharmacodynamics

- Blood samples for determination of serum drug concentrations and PD assessments (free and total C5) will be collected before and after administration of study drug at the time points specified in the SoA (Section 1.3).
- Instructions for the collection and handling of biological samples will be provided by Alexion. The actual date and time (24-hour clock time) of each sample will be recorded.
- Additional information on sample collection, including blood volume requirements, is provided in the Laboratory Manual.

- The Day 1 baseline PK and PD blood samples will be collected at predose, within 90 minutes before administering study drug at visits specified in the SoA (Section 1.3). The predose blood sample may be drawn through the venous access created for the dose infusion, prior to administration of the dose.
- For all subsequent visits falling on dosing days, samples will be collected predose (within 0.5 hours prior to the start of infusion). In order to minimize needle sticks to the participant, the predose sample may be drawn through the venous access created for the dose infusion, prior to administration of the dose.
- Postdose PK and PD blood samples will be collected within 0.5 hours after completing study drug infusion. The postdose blood samples will be drawn from the participant's opposite, noninfused arm.
- For indicated visits not falling on dosing days, samples may be collected at any time that visit day.
- In the event of an unscheduled visit, PK and PD blood sample will be collected as soon as possible.
- Ravulizumab PK in urine may be conducted as an exploratory analysis based on findings from impact of proteinuria on serum PK.

Study intervention concentration information that may unblind the study will not be reported to investigative sites or blinded personnel until the study has been unblinded.

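### The PK rule for BLQ values drops isolated on-treatment troughs because of their position in the sampling sequence, which can only push trough summaries upward (minor, descriptive PK only)

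*SAP*

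**What the plan says.** SAP 5.7.1 limits the rule to table statistics ("For the calculation of summary statistics"). A BLQ concentration counts as LLOQ/2, "unless a BLQ value falls between 2 measurable values, in which case it will be omitted". The section makes no distinction between predose and other samples and does not say whether *between* means adjacent samples or any earlier and any later sample. It also provides for individual data: "A listing of serum ravulizumab concentration will be presented", with BLQ values marked as below LLOQ. Free and total C5 are summarized in the same section without a corresponding rule.

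Protocol 1.3 sets the sampling. On dosing days with a PK entry, "PK/PD samples will be collected predose (within 0.5 hours prior to the start of infusion) and at EOI", and protocol 8.7 confirms the timing: "Postdose PK and PD blood samples will be collected within 0.5 hours after completing study drug infusion". In the rows headed "Blood samples for PK/PD", both cohorts have paired trough and end-of-infusion samples at Weeks 2, 10 and 18, and a trough alone at Week 26. The Extension tables show no post-dose PK sample at Week 26. Pairs resume at Weeks 34 and 42 (LN) or Weeks 28, 36 and 44 (IgAN), and Week 50 is the last sample. Protocol 4.3 gives a trough above 175 ug/mL as the exposure target behind the dose.

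**The concern.** Dropping a BLQ value that lies between measurable ones treats it as an assay anomaly. That suits a single concentration curve after one dose. Under repeated dosing, a low trough followed by a high end-of-infusion sample is the expected pattern, so the exception catches genuine troughs as well as errors.

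Characterizing PK/PD is a study objective, and protocol 4.3 makes end-of-interval concentration the measure that matters. A BLQ trough on treatment is the most extreme value that measure can take. If such values occurred, the by-visit trough tables would leave them out, while free C5 from the same visit would stay in.

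Treatment also varies with position. In LN, the Week 50 sample is taken 8 weeks after the Week 42 dose (50 − 42 = 8), just as the Week 42 trough is taken 8 weeks after the Week 34 dose. A BLQ result is kept at Week 50 and dropped at Week 42. At Week 28 in IgAN the rule works in opposite directions in the two treatment sequences.

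**Working it through.** The plan states no figure on this point, so there is none to reproduce. The check has three parts.

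**1. Which troughs the rule omits.** The neighbouring samples come from protocol Tables 1 to 4. Each row assumes one isolated BLQ result, with all other post-dose samples measurable.

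| Sample | Sample before | Sample after | Result |
|---|---|---|---|
| Day 15, both cohorts | Day 8 (Day 1 end of infusion if the Week 1 visit is not held) | Day 15 end of infusion | omitted |
| Week 10, both | Day 29 | Week 10 end of infusion | omitted |
| Week 18, both | Week 10 end of infusion | Week 18 end of infusion | omitted |
| Week 26, both | Week 18 end of infusion | next trough (Week 34 LN, Week 28 IgAN) | omitted |
| Week 34, LN | Week 26 trough | Week 34 end of infusion | omitted |
| Week 42, LN | Week 34 end of infusion | Week 42 end of infusion | omitted |
| Week 28, IgAN ravulizumab group | Week 26 trough | Week 28 end of infusion | omitted |
| Week 28, IgAN placebo switchers | none measurable | Week 28 end of infusion | kept at LLOQ/2 |
| Week 36, IgAN | Week 28 end of infusion | Week 36 end of infusion | omitted |
| Week 44, IgAN | Week 36 end of infusion | Week 44 end of infusion | omitted |
| Week 50, both | Week 42 (LN) or Week 44 (IgAN) end of infusion | none | kept at LLOQ/2 |

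For a participant continuously on ravulizumab, that is 6 of 6 LN trough visits and 7 of 7 IgAN trough visits before Week 50.

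If every trough in a participant is BLQ, the answer depends on the undefined word. Reading *between* as any earlier and any later measurable sample omits all troughs before Week 50. Reading it as adjacent samples keeps Weeks 26 and 34 (LN) or Weeks 26 and 28 (IgAN) at LLOQ/2 and omits the rest.

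**2. Direction.** A measurable value is at least LLOQ, so a retained BLQ at LLOQ/2 is the lowest value at its visit. Leaving it out cannot lower the mean, geometric mean, median or minimum.

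**3. Size, on assumed inputs.** Take n = 40 troughs at a visit (the planned ravulizumab arm per cohort), k of them BLQ, and GM the geometric mean of the measurable ones. Then:

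- geometric mean kept ÷ geometric mean omitted = (LLOQ / (2·GM))^(k/n)
- arithmetic mean kept ÷ arithmetic mean omitted = ((n − k) + k·LLOQ/(2·mean)) / n

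The LLOQ, the typical trough and k are not in the documents. With k = 2 and GM = 500 ug/mL (all assumed):

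- LLOQ 1: 500 × (0.5/500)^(2/40) = 354, and 500/354 = 1.41
- LLOQ 5: 500 × (2.5/500)^(2/40) = 384, and 500/384 = 1.30
- LLOQ 10: 500 × (5/500)^(2/40) = 397, and 500/397 = 1.26

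With LLOQ from 5% down to 0.1% of the GM (for the arithmetic column, of the mean of the measurable troughs), omission overstates the summaries as follows:

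| BLQ troughs out of 40 | Geometric mean | Arithmetic mean |
|---|---|---|
| 1 | 10% to 21% | 2.5% to 2.6% |
| 2 | 20% to 46% | 5.1% to 5.3% |
| 4 | 45% to 114% | 10.8% to 11.1% |

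**The case against.** The best defence is that this is a convention with limited reach. The listing shows every BLQ value, the planned number of observations exposes omissions at a visit, and individual profiles may be plotted. The median is planned and barely moves for two values in 40. Dose adequacy has its own review of the first 10 treated participants (SAP 5.8.1). The antibody has an extended half-life (protocol 2.1), so an isolated BLQ value may well be a sampling or labelling error. LLOQ/2 is itself an arbitrary constant. All of that stands and keeps the point small. It does not justify deciding validity by position, because the rule asks for no evidence of error.

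A reader might infer more than the documents support:

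- *That the rule removes exactly the troughs showing lost exposure.* It does not. Troughs that are measurable but at or below 175 ug/mL show reduced exposure too, and all of them stay in.
- *That every trough sits between two end-of-infusion samples.* Only Weeks 18 and 42 (LN) and Weeks 18, 36 and 44 (IgAN) do, plus Day 15 when the Week 1 visit is not held. The omission needs only measurable samples on both sides.
- *That protocol 4.3 voices a fear about the study dose.* Its remark that clearance "may result in inadequate levels of C5 suppression in patients with" the heavier weight groups concerns the labeled PNH/aHUS regimen. The same section predicts study exposures similar to those in Phase 3.
- *That the rule distorts a planned coverage rate.* With two BLQ troughs and the other 38 above target, coverage would read 38/38 = 100% instead of 38/40 = 95%. But SAP 5.7.1 plans no such proportion, and the 97.5th percentile in protocol 4.3 is a simulation criterion for choosing doses.
- *That PK and PD tables resting on different participants is a defect in itself.* The SAP already defines separate PK and PD analysis sets.

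**Conclusion.** The point holds as a minor one about descriptive PK. For participants continuously on ravulizumab, an isolated BLQ trough is omitted from the summary statistics at every trough visit before Week 50 when earlier and later samples are measurable. The same result at Week 50, or at Week 28 in IgAN placebo switchers, is kept at LLOQ/2. Any effect on the mean, geometric mean, median or minimum is upward.

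The schedule result follows from the protocol tables as they read. The size does not: it rests on an assumed LLOQ, trough level and BLQ count, and BLQ troughs should be rare. If none occurs, the rule changes nothing. If a few occur, the geometric mean is the statistic most affected. No efficacy, alpha or power figure changes.

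**What to change.** In SAP 5.7.1, replace the positional exception with the following: BLQ predose troughs after the first ravulizumab dose are set to LLOQ/2 wherever they fall in the sequence, and a value is omitted only when an assay or sampling error is documented. For IgAN placebo participants, count from their first ravulizumab dose at Week 26. If any positional rule is retained for other samples, define *between*.

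Add to the PK table, per trough visit, the number of BLQ troughs and the number at or below 175 ug/mL.

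The cost is one sentence and two table rows, using data already collected. The downside is that the geometric mean and CV become sensitive to LLOQ/2 whenever BLQ values occur, so they should be read alongside the planned median.

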5.7.2. Immunogenicity Analyses

All immunogenicity analyses will be performed on the Safety Set.

The incidence of ADAs to ravulizumab will be summarized descriptively separately for each disease cohort by treatment group at baseline and each postbaseline time point. Immunogenicity variables include ADA status categories, ADA response categories, ADA, or neutralizing antibody (NAb) incidence and titer over the duration of the study as follows:

ADA status categories:

- **ADA negative:** An ADA-negative signal in the ADA assay at all timepoints collected for ADA analysis
- **ADA positive:** An ADA-positive signal in the ADA assay at any timepoint collected for ADA analysis

Participants who are ADA positive may be further categorized into ADA response categories as follows:

- **Pre-existing immunoreactivity:** An ADA-positive response with either of the following 2 conditions met:
 - ADA-positive response at baseline with all post-first-dose ADA results negative
OR
 - ADA-positive response at baseline with all post-first-dose ADA responses less than 4-fold over the baseline titer level
- **Treatment-emergent ADA responses:** An ADA-positive response post-first-dose when baseline results are negative or missing
- **Treatment-boosted ADA responses:** An ADA-positive response post-first-dose that is \geq 4-fold over the baseline titer level when the baseline result is positive

Treatment-emergent or treatment-boosted ADA responses may be further categorized as follows:

- **Persistent:** ADA responses with 2 or more consecutive ADA-positive samples separated by at least a 16-week period, with no ADA-negative samples in between, irrespective of missing samples
- **Indeterminate:** ADA-positive sample only at the last collected sample
- **Transient:** ADA response that is neither a persistent nor an indeterminate response

ADA-positive samples will be further characterized for neutralizing activity in the NAb assay. NAb status categories are as follows:

- NAb positive
- NAb negative

Associations between ADA response categories and serious and severe adverse events may be explored, including SAEs like systemic hypersensitivity, anaphylaxis, injection/infusion site reactions lasting more than 24 hours, and other immune related SAEs.

Associations between ADA response categories and key efficacy endpoints or variables may be explored to assess the potential impact of immunogenicity on drug efficacy.

All ADA samples will be provided along with titer values in by-participant listings.

